6.5.3 Baseline descriptive analyses

We will report the means and frequencies of baseline variables for eligible patients.

6.5.4 *Exploratory analyses*

In subsequent analyses, we will develop a model to predict intervention responsiveness based on observable patient characteristics. We will fit separate logistic and boosted regression models using sets of these predictors to evaluate the ability to predict responsiveness to each messaging type. Boosted regression is a machine learning method robust to multi-collinearity and overfitting.^{19,20} For each, we will use 10-fold cross-validation to compare C-statistics for the ability to predict intervention response and calculate a continuous net reclassification index to assess changes in predicted response with additional predictors.^{21,22} We will also measure the relative influence of predictors to determine those that are most influential at predicting intervention responsiveness for a given arm.

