2. SPECIFIC AIMS

The main aims are to 1) test the effect of “how” vs “why” framed messages on the rates of COVID-19 booster vaccination and 2) assess association of clinical and demographic characteristics with intervention responsiveness.

The objectives and endpoints for this project are summarized below.

OBJECTIVES	ENDPOINTS	JUSTIFICATION FOR ENDPOINTS
Aim 1		
To test the effect of “how” vs “why” framed messages on the rates of COVID-19 vaccination	Primary : the rate of booster vaccination at the targeted visit Secondary : the rate of receipt of a COVID booster vaccine within 6 weeks of the targeted visit	These outcomes are directly related to the interventions, are clinically meaningful, and are measurable using routinely collected data in the Mass General Brigham COVID-19 Vaccine Registry and the Research Patient Data Registry (RPDR) and/or Epic Enterprise Data Warehouse (EDW). We plan to use RPDR for variable collection as long as all the variables needed are available in the RPDR. If a variable is not available in the RPDR then we will supplement with use of the EDW for those variables.
Aim 2		
To assess association of clinical and demographic characteristics with intervention responsiveness	A model to predict likelihood of response to each intervention based on patient characteristics	A model predicting intervention responsiveness could be used to tailor future interventions to specific patients

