5.3 Study Schema

5.4 Scientific rationale for study design

The use of a randomized trial design will be able to both provide stronger evidence of causality in the effectiveness of the interventions and allow for empiric derivation of patient characteristics that may influence intervention responsiveness. An observational study design or patient self-report of factors that influence intervention responsiveness are more subject to bias.

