6.4 Samples size determination

Sample size estimates suggest that ~1,100 individuals in each arm will allow us to observe a 5% difference in vaccination rates compared to the usual care arm, assuming a usual care arm vaccination rate of 20% as well as assumptions of alpha=0.05 and power=0.80. Given that more than 1 million patients receive care at MGB, we expect to identify at least 5,000 patients who have not yet received the booster vaccination at the outset of the trial and who will be eligible to receive one of the messages. This will also provide sufficient power for secondary outcomes. Under the same assumptions, we should be able to observe a <6% difference in 6-week vaccination rates compared to usual care, assuming a usual care arm vaccination rate of 25%.

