6.5 Statistical analyses

6.5.1 Analysis of the primary endpoint

The primary outcome will be the rate of receipt of COVID booster vaccine dose in each arm at the target primary care outpatient appointment, treated as a binary outcome. We will use logistic regression to compare outcomes between each intervention arm versus usual care and against each other. Of note, we chose not to formally adjust for multiple testing in the primary analysis for several reasons. First, although the chance of finding at least one false positive among several tests is >5%, a Bonferroni correction would be much too conservative in this case, because the multiple comparisons among the treatment arms share the same four exposure groups. Second, a recent systematic review of multiple arm trials showed that more than half of all randomized trials with multiple exposure groups do not adjust for multiple comparisons,¹⁸ reasoning that if each exposure was compared with control in a separate trial, no adjustment would be necessary.

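### Aim 2 never defines response or states a usual-care contrast, so its models may predict who is vaccinated given a message, not because of it

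*Combined protocol and SAP*

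**What the plan says.** Section 2 (Specific Aims) lists the association of patient characteristics with intervention responsiveness as the second of two main aims. Its endpoint is "A model to predict likelihood of response to each intervention based on patient characteristics", meant for tailoring later messages. Section 5.4 gives as one reason for randomising that the design will "allow for empiric derivation of patient characteristics that may influence intervention responsiveness".

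The analysis is in section 6.5.4 (Exploratory analyses). It plans "separate logistic and boosted regression models using sets of these predictors to evaluate the ability to predict responsiveness to each messaging type", uses 10-fold cross-validation to "compare C-statistics for the ability to predict intervention response", adds a continuous net reclassification index (NRI), and looks for the predictors that are "most influential at predicting intervention responsiveness for a given arm".

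No section defines response or responsiveness, says whether it refers to the targeted visit or to 6 weeks, or gives the usual-care arm a part in Aim 2. Aim 1 differs: sections 6.5.1 and 6.5.2 both "compare outcomes between each intervention arm versus usual care and against each other".

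**The concern.** Responding to a message means being vaccinated because of it. That is a contrast between two conditions, and only one of them is observed in any patient. The C-statistic and the NRI both need an observed label for each patient, and the only one available is vaccination status. On the natural reading, though the text does not say so outright, the models would estimate uptake given a message.

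Uptake and benefit are different quantities. Patients with high uptake under a message may gain the most, gain the same as others, or gain nothing because they would have come forward anyway. Which of these holds depends on how the message effect varies with baseline propensity, and the stated measures carry no information on that. Later tailoring based on these models could be aimed at patients who need no message. A good C-statistic would give no warning.

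**Working it through.** **Inputs from the plan.** Section 6.4 assumes 20% vaccinated in usual care, a 5-point difference (so 25% with a message), about 1,100 per arm, and "assumptions of alpha=0.05 and power=0.80". It expects at least 5,000 eligible patients; split 1:1:1 (section 4.3) that is 5,000/3 ≈ 1,667 per arm. The documents give no subgroup rates, so those below are assumptions.

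**The plan's own figure.** Two-sided test, pooled variance under the null, no continuity correction:
n = [1.96·√(2·0.225·0.775) + 0.8416·√(0.20·0.80 + 0.25·0.75)]² / 0.05² = (1.1575 + 0.4961)² / 0.0025 ≈ 1,094 per arm. This reproduces the stated 1,100 or so, and the sample size is not in dispute.

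**Who makes up the vaccinated in a message arm.** Let d be the share of all patients whom the message deters. Then P(vaccinated without the message | vaccinated with it) = (0.20 − d)/0.25.

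| d | share vaccinated anyway |
|---|---|
| 0 | 80% |
| 1% | 76% |
| 2% | 72% |
| 5% | 60% |

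With d = 0 and 1,100 patients, 275 are vaccinated, of whom 220 would have been anyway and 55 are the gain.

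**Can the C-statistic tell benefit from uptake?** Take two equal groups with message-arm uptake of 35% and 15% (mean 25%). Using group as the predictor:
- sensitivity = 0.35/(0.35 + 0.15) = 0.70
- false-positive rate = 0.65/(0.65 + 0.85) = 0.433
- C = 0.5 + 0.5·(0.70 − 0.433) = 0.633

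Usual-care rates do not enter. Three usual-care patterns, each averaging 20%, give:

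| Usual care | Gains (points) | Message-arm C | Difference in gains | 95% half-width at 1,667 per arm |
|---|---|---|---|---|
| 35% / 5% | 0 / +10 | 0.633 | −10 | 5.4 |
| 30% / 10% | +5 / +5 | 0.633 | 0 | 5.5 |
| 25% / 15% | +10 / 0 | 0.633 | +10 | 5.6 |

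The half-width is 1.96·√(Σp(1 − p)/833.5) over the four cells. For the middle row: 1.96·√(0.655/833.5) = 0.055. All half-widths here assume independent patients, whereas section 4.3 randomises by visit day, so they are lower limits. In 2,000 simulated trials per row, mean C was 0.633 each time, and the mean difference in gains was −10.0, −0.1 and +10.0 points.

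**Second check, with a continuous predictor.** One standard-normal predictor, 20% baseline, logit slope 0.5, 1.0 or 1.5. When the message affects nobody, the within-arm C-statistic is still 0.64, 0.74 or 0.82.

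**Precision of the proper contrast.** The half-width for 20% vs 25% in a group with m patients per arm is 1.96·√((0.16 + 0.1875)/m).

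| | halves | thirds | fifths |
|---|---|---|---|
| 1,667 per arm | 4.0 | 4.9 | 6.3 |
| 1,100 per arm | 4.9 | 6.0 | 7.8 |

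Power to detect gains of 2.5 vs 7.5 points in two equal groups, with usual care at 20% in both: the variance sum is 0.16 + 0.16 + 0.1744 + 0.1994 = 0.6938. At 833.5 per cell SE = 0.0288, so power = Φ(0.05/0.0288 − 1.96) ≈ 0.41. At 550 per cell it is 0.29.

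**The case against.** The strongest reply is that the plan is under-specified rather than wrong. Separate models may simply mean two model types, a given arm may include usual care, and section 5.4 links responsiveness to randomisation, so a between-arm analysis may be intended. That is possible. But if it is intended, the C-statistic and NRI would not evaluate it, so section 6.5.4 needs changing on either reading.

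Second, choosing between *how* and *why* for a patient needs only the two message models, and section 4.1 calls the intervention very cheap, so messages need not be rationed. This stands in part: usual care is not required for that one choice. The differencing is still not stated, and discrimination within one arm does not assess it.

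Third, uptake may track benefit. With a constant odds ratio of 1.33 (20% to 25%), usual-care rates of 10% and 30% become 12.9% and 36.4%, gains of 2.9 and 6.4 points, so the two rankings agree. This is a fair case, but whether it applies is what Aim 2 should find out, and the stated measures cannot.

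Finally, the trial is a pilot, the analysis is labelled exploratory, and an interaction analysis will be imprecise. All true, and these points limit the weight of the concern. A wide interval on the right quantity is still more useful than a precise answer to another question.

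**Conclusion.** The concern holds. Followed as written, section 6.5.4 would score how well vaccination is predicted and could not show which patients a message helps, although that is a named main aim. This should be corrected. It does not threaten the primary or secondary analysis.

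The 80% ceiling rests only on the planning rates in section 6.4. The subgroup illustration rests on assumed rates; it shows that one C-statistic is compatible with a reversed, flat or correct ranking on the absolute scale, not that a reversal will occur. Fitting models by arm is not itself the fault. What is missing is a definition of response, a usual-care model and the step that takes differences between arms.

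**What to change.** In section 6.5.4:
- Name the outcome and time point (targeted visit, 6 weeks, or each separately).
- Define responsiveness as the between-arm difference in vaccination probability: each message versus usual care, and *how* versus *why*.
- Estimate it from all three randomised arms, either with arm-by-covariate terms or with arm-specific logistic or boosted models, usual care included, differenced for each patient.
- Assess it by cross-validated agreement between predicted and observed between-arm differences in a few groups of predicted benefit, such as halves or thirds, rather than by the C-statistic or NRI for vaccination alone.
- Label any within-arm models as uptake models.

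The cost is SAP wording and modest programming on data already collected. The drawback is the limited precision shown in the working, further reduced by visit-day clustering. Aim 2 may find little heterogeneity, and the SAP should say so in advance.

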5.2.2 Aim 2 Design

In Aim 2, we will assess association of clinical and demographic characteristics with intervention responsiveness. To do this, we will measure baseline patient clinical, historical, and demographic characteristics. Characteristics measured from the RPDR/EDW will include age, gender, race, prior influenza vaccine history, and comorbidities that increase risk of severe COVID disease, among others. We will also measure zip-code linked variables including mean household income, education level, rurality, and prevalence of COVID in the patient's surrounding community. We will develop models that predict which patients are most likely to respond to each intervention using patient baseline characteristics, which in the future could allow for targeting of interventions to specific patients.

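### For the logistic models in section 6.5.4, the continuous net reclassification index tends to come out positive when uninformative predictors are added, so it is a misleading measure of what extra predictors contribute to the exploratory Aim 2

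*Combined protocol and SAP*

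**What the plan says.** Section 2 lists the prediction of intervention responsiveness as the second of two main aims. Section 6.5.4 places the work under exploratory analyses: "In subsequent analyses, we will develop a model to predict intervention responsiveness based on observable patient characteristics". Two model classes are planned: "We will fit separate logistic and boosted regression models using sets of these predictors". The candidate list in section 5.2.2 is open-ended, "age, gender, race, prior influenza vaccine history, and comorbidities that increase risk of severe COVID disease, among others", and zip-code variables are added to it.

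For performance, section 6.5.4 states that "we will use 10-fold cross-validation to compare C-statistics for the ability to predict intervention response". The same sentence goes on to say that the team will "calculate a continuous net reclassification index to assess changes in predicted response with additional predictors". This index is the only measure the plan ties explicitly to added predictors. The plan gives no threshold or test for it, no rule for when it disagrees with the C-statistic, and no calibration check or proper score. The wording can be read with or without cross-validation applying to the index.

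**The concern.** The continuous index counts every upward move in predicted risk among events and every downward move among non-events, however small. A logistic model with surplus parameters tends to overfit and stretch its predictions: patients already at high predicted risk move up, and they hold a larger share of the events. The index can then rise although the added variables carry no information, and testing on held-out patients does not fully remove this.

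Aim 2 is meant to inform which patients should receive which message in future. With an open-ended predictor list, some candidates will probably be uninformative. If the measure reported for added predictors leans positive for them, the results could suggest value that is absent and contradict the C-statistic printed beside it.

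**Working it through.** **Inputs from the documents.** Section 6.4: "1,100 individuals in each arm will allow us to observe a 5% difference in vaccination rates", with 20% vaccinated under usual care (hence 25% in a message arm), alpha 0.05 and power 0.80. At least 5,000 patients are expected; at 1:1:1 that is 5,000/3 = 1,667 per arm. Section 6.5.4: ten folds, logistic and boosted models.

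**Assumptions, because the documents give no figure.** Five real predictors; 1 to 20 noise predictors; base C-statistic 0.60 to 0.85; a binary outcome within one arm; boosting settings.

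**The plan's own figure.** With pooled proportion 0.225 and two-sided alpha:

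n = [1.96 × √(2 × 0.225 × 0.775) + 0.8416 × √(0.20 × 0.80 + 0.25 × 0.75)]² / 0.05² = (1.1575 + 0.4961)² / 0.0025 ≈ 1,094 per arm.

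The stated figure of about 1,100 is reproduced, and power at 1,100 is 0.802. It serves here only as the simulation size.

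**Measure.** Index = mean of sign(new − old risk) in events minus the same mean in non-events. z = index / √(v₁/n₁ + v₀/n₀), where v is the variance of the signs and n₁, n₀ are the numbers of events and non-events.

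**Logistic models, n = 1,100, 25% events, base C-statistic 0.76, 10-fold cross-validated, 2,000 datasets per row:**

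| Noise predictors added | Mean index | Index > 0 | z > 1.96 | Mean change in C | C falls | Index > 0 and C falls | Brier worsens |
|---|---|---|---|---|---|---|---|
| 1 | +0.012 | 60% | 7.1% | −0.0006 | 79% | 39% | 80% |
| 5 | +0.026 | 63% | 10.2% | −0.0034 | 88% | 52% | 91% |
| 10 | +0.038 | 67% | 13.6% | −0.0067 | 94% | 61% | 96% |
| 20 | +0.054 | 72% | 18.2% | −0.0131 | 98% | 70% | 99% |

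**Where the excess comes from (last row).** With 275 events and 825 non-events the nominal standard error is at most √(1/275 + 1/825) = 0.0696. The Monte Carlo error of 0.0020 implies an actual SD of 0.0020 × √2,000 = 0.089.
- No lean: P(z > 1.96) ≈ P(Z > 1.96 × 0.0696/0.0894) = P(Z > 1.53) ≈ 6%.
- Mean +0.054: P(Z > (0.1365 − 0.0540)/0.0894) = P(Z > 0.92) ≈ 18%, matching the table.

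So part of the excess is an understated standard error, and the larger part is the lean.

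**Other base strengths (logistic, cross-validated):**
- Base C about 0.60 to 0.61: positive in 51% to 56%. Mean +0.001 to +0.011 at 0.61. Nearly no lean.
- Base C 0.67, 20 noise predictors (400 datasets): positive in 64%, z > 1.96 in 9%, C falls by 0.018.
- Base C 0.69: mean +0.006, +0.017 and +0.027 for 1, 5 and 20 noise predictors; positive in 57% to 63%.
- Base C 0.74, 20 noise predictors (two runs, 300 and 400 datasets): mean +0.046 and +0.049, positive in 71% and 72%, z > 1.96 in 14% and 15.5%, C falls by 0.014 and 0.015.
- Base C 0.85: mean +0.024 to +0.116; positive in 62% to 90%.
- n = 1,667, base C 0.70 to 0.76, 5 or 20 noise predictors: positive in 59% to 73%.

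**Index on the fitting data.** Mean +0.05 to +0.34 across settings. With 20 noise predictors the mean was +0.26 to +0.28 and z > 1.96 in 98% to 99% at every base C tested in the 400-dataset runs, so a weak base model gives no protection.

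**Boosted regression (60 datasets in each of five settings, n = 1,100, cross-validated).** Mean index −0.05 to −0.30; positive in 0% to 23%. C fell by 0.008 to 0.025 and the mean Brier score worsened in all five.

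**The alternative measure.** In the logistic runs of 400 datasets, cross-validated log-likelihood improved in only 7% to 10% with 5 noise predictors and in 0% to 0.25% with 20.

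**The case against.** A reader might infer that the plan will formally accept noise predictors because their index is positive. The documents do not support that. Section 6.5.4 has no threshold, test or keep-or-drop rule, so the rates of z above 1.96 describe a test that an analyst might apply, not one the plan proposes. The same sentence compares cross-validated C-statistics, which fell in most noise runs, so the planned output would usually carry its own warning. That stands. What it leaves open is which measure prevails when the two disagree, and the index is the one named for added predictors.

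A reader might also infer that the index flatters noise in any model. It does not: the lean almost disappears with a weak base model, and for boosted regression the index was negative. The boosted check is small and its tuning is assumed, but it is the only evidence on that model class. Nor does it rescue the index, whose direction then depends on the model class as well as on what the predictors carry.

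The base C-statistic and the number of noise predictors are not in the documents, and section 5.2.2 names only about nine characteristics or domains before leaving the list open. The size is therefore conditional. Finally, putting both measures under cross-validation is the more natural reading of the sentence, so the fitting-data figures show what the ambiguity could cost, not what the plan says it will do.

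**Conclusion.** The concern holds for the logistic models, in an analysis labelled exploratory. At 1,100 per arm and an assumed base C-statistic of about 0.67 to 0.76, the cross-validated index is positive for pure noise in roughly 57% to 72% of datasets. Its z value exceeds 1.96 in about 9% (base C 0.67) to 18% (base C 0.76) when 20 noise predictors are added, against a nominal 2.5%.

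The consequence is a misleading figure for incremental value that can contradict the C-statistic, not a formal false endorsement. Only a binary outcome within one arm was simulated. Section 6.5.4 does not define responsiveness, and a model of the contrast between arms was not examined. The Aim 1 comparisons are unaffected.

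**What to change.** In section 6.5.4, replace the continuous net reclassification index with the change in cross-validated log-likelihood (or Brier score), computed on the same ten folds for both logistic and boosted models, and name it as the measure of whether added predictors help. If the index is kept, state that it is computed only on held-out predictions and reported as secondary to that score.

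The score is not infallible for a single variable: with one noise predictor the Brier score still failed to worsen in about 20% of datasets (100% − 80%), so very small improvements deserve caution.

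The cost is a sentence or two in the plan and a few lines of code, with no new data. The downside is some loss of comparability with earlier reports that used the index.

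### Relative influence, as usually computed, favours many-valued predictors, so the exploratory ranking in section 6.5.4 can place noise zip-code variables above a real gender or race effect

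*Combined protocol and SAP*

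**What the plan says.** Section 6.5.4 of the combined protocol and SAP plans two model types: "We will fit separate logistic and boosted regression models using sets of these predictors". Performance is assessed out of sample: "we will use 10-fold cross-validation to compare C-statistics for the ability to predict intervention response". The same sentence adds a continuous net reclassification index for added predictors. The section then closes with the ranking: "We will also measure the relative influence of predictors to determine those that are most influential at predicting intervention responsiveness for a given arm". That closing sentence gives no formula, no held-out step and no noise reference. The only safeguard stated for the boosted models is "Boosted regression is a machine learning method robust to multi-collinearity and overfitting".

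Section 5.2.2 lists the candidate predictors. The patient-level ones "will include age, gender, race, prior influenza vaccine history, and comorbidities that increase risk of severe COVID disease, among others". To these the plan adds "zip-code linked variables including mean household income, education level, rurality, and prevalence of COVID". Coding is not given for any of them. Tree depth, number of trees, learning rate and a tuning rule are not given either.

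**The concern.** Each split in a boosted tree is chosen because it gives the largest gain on the data being fitted. A predictor with many distinct values offers many candidate cut points and so more chances of a large gain by luck. A yes/no predictor offers one. Summing these gains over all trees therefore favours many-valued predictors even when they carry no information. Rescaling to 100% means that something always heads the list. Robustness to overfitting, even if granted, concerns prediction and does not protect a ranking built from in-sample gains.

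The predictor list in section 5.2.2 mixes the two types. Sections 1 and 5.5 motivate Aim 2 by differences in hesitancy by age, gender and race. Two of these three are likely to be few-valued, so the measure works against them. A reader of the Aim 2 results could be told that community income or COVID prevalence is among the most influential characteristics when it is noise, while a real gender or race effect sits below it.

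**Working it through.** **Inputs from the documents.** Section 6.4: about 1,100 per arm, usual-care rate 20%, difference of 5 points, alpha 0.05, power 0.80, at least 5,000 eligible. Section 4.3: 1:1:1 allocation, so 5,000/3 = 1,667 per arm if all are enrolled. Sections 5.2.2 and 6.5.4: predictors and models as above.

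**Step 1. The plan's own figure.** Two-sided test, pooled variance under the null:

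n = [1.96·√(2·0.225·0.775) + 0.8416·√(0.20·0.80 + 0.25·0.75)]² / 0.05² = (1.1575 + 0.4961)² / 0.0025 = 1,094.

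This agrees with about 1,100, and power at 1,100 is 0.802. The arm size is therefore a sound basis for the simulations.

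**Step 2. The measure.** For predictor j, RI_j = 100 × (gain summed over all splits on j) / (gain summed over all splits). The RI_j sum to 100 by construction, whatever the model's C-statistic.

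**Step 3. Simulation assumptions (not in the documents).** One arm; mean vaccination rate 25% (20% plus the 5-point target); nine predictors: age, gender, race as a 20% indicator, influenza vaccination history, comorbidity count, and four zip-level variables over 150 zip codes that are pure noise. Trees use subsample 0.5 and minimum leaf 10. The only true effect, if any, is on gender or race.

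**Step 4. No true effect** (n = 1,100, depth 3, 100 trees, learning rate 0.1, 200 runs). An even share would be 100/9 = 11.1% each, or 44.4% for the four zip variables. Instead the zip variables took 62%, gender 2.8% and race 1.9%.

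**Step 5. True 10-point effect, fixed tree count** (200 runs each). A direct comparison of 20% with 30% in 550 per gender has power Φ[(0.10·√550 − 1.96·√(2·0.25·0.75)) / √(0.16 + 0.21)] = Φ(1.88) = 0.97, so this effect is easy to see by other means.

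| True effect | n | Depth | Trees, rate | Its share | Top zip share | Some zip variable ranks above it |
|---|---|---|---|---|---|---|
| Gender | 1,100 | 3 | 100, 0.1 | 4.9% | 17% | 100% |
| Race | 1,100 | 3 | 100, 0.1 | 3.6% | 17% | 100% |
| Gender | 1,667 | 3 | 100, 0.1 | 5.6% | 17% | 100% |
| Gender | 1,100 | 1 | 100, 0.1 | 11.4% | 21.5% | 94% |
| Race | 1,100 | 1 | 100, 0.1 | 8.5% | 22% | 99% |
| Gender | 1,100 | 1 | 300, 0.01 | 22.7% | 20.9% | 43% |

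**Step 6. Tuned tree count and held-out permutation** (scikit-learn, 60 runs each, gender effect). Entries are the percentage of runs in which at least one noise zip variable outranks gender.

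| Effect | n | Depth, rate | Split gain, 100 trees | Split gain, tuned | Held-out permutation |
|---|---|---|---|---|---|
| 5 points | 1,100 | 3, 0.1 | 100 | 97 | 78 |
| 10 points | 1,100 | 3, 0.1 | 100 | 80 | 32 |
| 10 points | 1,100 | 3, 0.02 | 100 | 88 | 15 |
| 10 points | 1,667 | 3, 0.1 | 100 | 65 | 17 |
| 10 points | 1,100 | 1, 0.1 | 97 | 32 | 17 |
| 15 points | 1,100 | 3, 0.1 | 100 | 35 | 0 |

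With 60 runs the Monte Carlo standard error is about √(0.32·0.68/60) = 6 points at 32%.

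**Step 7. A different predictor mix.** Four continuous and six binary predictors, n = 1,100, 22.5% events, 100 trees of depth 2. With no effect, the continuous predictors took 92–93% of influence. With one true binary predictor (12% prevalence, odds ratio 2.0), its mean rank was 5.0 of 10 and it was never first. Held-out permutation put it first in 68–73% of runs.

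**The case against.** The strongest case against the point is about consequence and size. Section 2 names the Aim 2 endpoint as a prediction model, and sections 5.2 and 5.2.2 tie future targeting to the models. The ranking is one closing sentence in an exploratory section of a self-described pilot. A reader might infer that it decides which patients receive tailored messages; the documents do not say so, and no selection step depends on it.

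The plan also has other evidence on individual predictors. Logistic coefficients have no cut-point bias: with the binary predictor of odds ratio 2.0 in step 7, a logistic model gave it the smallest p-value in 80% of runs in one set and 96% in another. The net reclassification index also speaks to added predictors.

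A reader might further infer that noise will always outrank a real demographic effect. That holds only under heavy fixed-tree settings, which the plan does not specify. In the step 7 scenario, 50 stumps put the true predictor first by relative influence in 28% of runs. A tuned tree count did so in 49% (stumps) and 18% (depth 2) of runs in which any tree was kept. Race may have several levels, and rurality and education may be categorical. That the measure uses the fitting data is inferred from common usage, since the plan leaves it undefined.

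All of this stands as a limit on size and importance. It does not remove the point. The plan assigns the naming of influential predictors to relative influence and not to the logistic estimates. Nothing in it secures the favourable settings, and tuning reduces the bias without removing it.

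**Conclusion.** The point holds, at low severity. If relative influence has its usual meaning, the ranking in section 6.5.4 is biased towards many-valued predictors and can place noise zip-code variables above a real gender or race effect at this trial's size. For a 10-point gender effect, this happened in about 100% of runs with 100 fixed trees of depth 3, and in 32% (depth 1) to 80% (depth 3) with a cross-validated tree count at learning rate 0.1. These rates rest on the assumed tuning, predictor coding, 150 zip codes and effect sizes.

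The documents do not support a wider conclusion. The cross-validated C-statistics, the logistic models and the primary comparison are unaffected, and the Aim 2 endpoint is the model rather than the ranking.

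**What to change.** Replace the closing sentence of section 6.5.4 with text such as:

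> Predictors will be ranked by permutation importance computed on the held-out folds of the planned 10-fold cross-validation, with the number of trees chosen by cross-validation within the training folds. All levels of a categorical predictor will be permuted together. The ranking will be reported beside the logistic model estimates. A predictor will be called influential only if its importance exceeds a null reference obtained by permuting the outcome and refitting (for example the 95th percentile of the maximum importance across predictors).

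Relative influence may stay as a descriptive display, with its definition and the tree settings stated.

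An interval over repeated fold splits is a tempting substitute for the null reference and should not be used. It reflects how one dataset was partitioned and ignores sampling error. On pure noise it flagged at least one predictor in 53–73% of 15 simulated datasets (depending on the interval), and in all 8 datasets of another set.

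The change needs no new data. It costs some extra computing, and fewer predictors, possibly none, will be named. It does not rescue small effects: for 5 points, where a direct test within an arm has only about 48% power, held-out importance still misranked gender in 78% of runs. The simulations did not test the outcome-permutation reference or the choice of tree count within training folds (step 6 chose it on the same ten folds), so the gain in step 6 is a guide and not a guarantee.
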